7.3 INTERVENTION VISITS

7.3.1 VISIT 3 (WITHIN 3 MONTHS OF DISCHARGE FROM HOSPITAL)

- This visit may be a telephone/video visit
- Initial visit by Amplio consultants
- Setup intervention visits schedules
- This visit is about 15 minutes.

7.3.2 VISIT 4 (10 DAYS \pm 5 DAYS AFTER VISIT 3)

- This visit may be a telephone/video visit
- Visit by Amplio consultants
- Initial assessment (Assessment#1) with care partner only
- This visit is about 60-90 minutes.
- Field notes will be collected

7.3.3 VISIT 5 (10 DAYS \pm 5 DAYS AFTER VISIT 4)

- This visit may be a telephone/video visit
- Visit by Amplio consultants

- 2nd assessment (Assessment#2) with care partner only
- This visit is about 60-90 minutes.
- Field notes will be collected

7.3.4 VISIT 6 (10 DAYS ± 5 DAYS AFTER VISIT 5)

- This visit is an in-home visit
- Visit by Amplio consultants
- Assessment#3 conducted with both care partner and PLWD
- This visit is about 2-3 hours.
- Field notes will be collected

7.3.5 VISIT 7 (10 DAYS ± 5 DAYS AFTER VISIT 6)

- This visit maybe an in-home visit or a virtual visit
- Visit by Amplio consultants
- Written care plan wil be provided and guidance on integration will be provided
- This visit is about 2-3 hours.
- Field notes will be collected

7.3.6 VISIT 8 (10 DAYS ± 5 DAYS AFTER VISIT 7)

- This visit maybe an in-home visit or a virtual visit
- Visit by Amplio consultants
- Touch points Assessment or follow-up with care partner and PLWD
- This visit is about 2-3 hours.
- Field notes will be collected

7.3.7 VISIT 9 (10 DAYS ± 5 DAYS AFTER VISIT 8)

- This visit maybe an in-home visit or a virtual visit
- Visit by Amplio consultants
- Touch points Assessment or follow-up with care partner and PLWD
- This visit is about 2-3 hours.
- Field notes will be collected

7.3.8 VISIT 10 (10 DAYS ± 5 DAYS AFTER VISIT 9)

- This visit maybe an in-home visit or a virtual visit
- This is an optional visit – only if needed by Amplio consultants, specifically based on touch point goals.
- Visit by Amplio consultants
- Touch points Assessment or follow-up with care partner and PLWD
- This visit is about 2-3 hours.
- Field notes will be collected

7.4 FINAL VISIT 11 (15-30 DAYS AFTER FINAL INTERVENTION VISIT 9/10)

- This visit is a virtual visit
- A REDcap survey is sent via email including the outcome measures CES-D-10, PSS, ZBI-12 and participant experience survey. In the case of participants unable to do via email, research staff will conduct this survey via a telephon/video visit
- A post-intervention interview will be conducted by research staff regarding experience of the participant in the study – via a telephone/video. This interview will be recorded (audio only)
- This visit is about 45 minutes

7.5 AD HOC VISITS (OPTIONAL AND AS NEEDED)

This visit can be a virtual visit or in-home visit. These are included to provide any additional support with regards to care plan implementation or any alternatives in the plan or provide additional resources or support to the dyads.

Participants will be asked to adhere to study visits and to complete study assessments. Participants will remain active unless withdrawn from the study. These will be documented in the relevant CRF.

8 STUDY ASSESSMENTS AND PROCEDURES

8.1 STUDY ASSESSMENTS FOR ENROLLED PATIENTS

8.1.1 DEMOGRAPHICS AND MEDICAL HISTORY

Demographic information will be collected, including: gender, age, race, ethnicity, height, weight, BMI, education, dementia diagnosis, co-morbidities (such as Diabetes, Hypertension) and e-mail address for consent.

8.1.2 CENTER FOR EPIDEMIOLOGIC STUDIES DEPRESSION SCALE-10 (CES-D-10)

The Center for Epidemiological Studies Depression Scale is an interview that evaluates caregiver depression through a self-report measure. Caregivers rate how they have experienced depressive symptoms in the past week, and survey scores are positively correlated with greater depressive symptoms (Radloff, 1977). The shorter 10 item version is validated in caregivers for dementia. The total score range from 0-30.

8.1.3 ZARIT BURDEN INTERVIEW-12

The Zarit Burden Inventory is an interview that evaluates caregiver burden through a self-report measure. The survey scores are positively correlated with behavior problems in older adults and depression scores of caregivers (Bedard et al., 2001). The shorter 12 item is validated in this population and total score ranges from 0-48. Higher the number, higher the burden.

8.1.4 PERCEIVED STRESS SCALE

The Perceived Stress Scale is a 10-item survey that evaluates perception of stress in the last month. The survey asks about how often someone had particular feelings and thought in the last month (0= never,

4= very often). The numerical response for question 4,5,7, and 8 is reversed (0 counts for 4 points), and then all the numerical responses are added together (Cohen, Kamarck, & Mermelstein, 1983).

8.1.5 INTERVENTION ASSESSMENTS

There are specific assessments for each of the intervention visits. These assessments will help evaluate and write the comprehensive care plan tailored to the dyad.

Specific assessments (see uploaded docs in the application) include

Assessment #1: With Care Partner Only

- Life Story
- Review Hospitalization info
- Review Diagnosis of Dementia
- Stress coping strategies

Assessment #2: With Care Partner Only

- Personal care/grooming
- Mobility
- Continence
- Eating Habits
- Sleep Pattern
- Senses
- Pain Intensity
- Assess Care Partners skill/approach
- Assess social support and self-care for care partners

Assessment #3: With Care Partner and PLWD

- Assess level of cognition, insight
- Review well-being, safety, comfort, depression/anxiety, sleep patterns, movement patterns, food/hydration plan
- Review environment for safety, including lighting, functionality, etc.
- Assess current purpose and engagement routine

Comprehensive Care Plan: With Care Partner and PLWD

- Written personalized care plan

Touch Point Assessment: With Care Partner and PLWD

- An opportunity to identify barriers and success associated with implementing the care plan, help improve competency.

- 2-3 touch points but will be based on involvement and challenges of the PLWD and care partners.

8.1.6 CARE EXPERIENCE SURVEY AND INTERVIEW

A 4 question survey is utilized to evaluate the program. In addition, a semi-structure 30 minute interview will be conducted by the research staff to understand the experience of the dyad in the study. This will be audio recorded and transcribed using software. The research staff will code the data and identify any themes to improve the intervention and study for a larger clinical trial

8.2 ADVERSE EVENTS AND SERIOUS ADVERSE EVENTS

8.2.1 DEFINITION OF ADVERSE EVENTS (AE)

An adverse event is any symptom, sign, illness or experience which develops or worsens in severity during the course of the study. Intercurrent illnesses or injuries should be regarded as adverse events. Abnormal results of diagnostic procedures are considered to be adverse events if the abnormality:

- Results in study withdrawal.
- Is associated with clinical signs or symptoms.
- Leads to treatment or to further diagnostic tests.
- Is considered by the investigator to be of clinical significance.

8.2.2 DEFINITION OF SERIOUS ADVERSE EVENTS (SAE)

Adverse events are classified as either serious or non-serious. A serious adverse event is any event that results in:

- Death.
- Life-threatening situation.
- Hospitalization or prolongation of hospitalization.
- Disability or incapacitation.

Other events determined by investigator to be medically significant in which subject's well-being is jeopardized (e.g. events that have high likelihood of escalating to the point of meeting criteria outlined above.

8.2.3 EXPECTEDNESS

PI will be responsible for determining whether an adverse event (AE) is expected or unexpected. An AE will be considered unexpected if the nature, severity, or frequency of the event is not consistent with the risk information previously described for the study intervention.

8.2.4 TIME PERIOD AND FREQUENCY FOR EVENT ASSESSMENT AND FOLLOW-UP

Upon consenting, a subject is considered to be a participant in the study, and until that person either withdraws or completes study, AEs and SAEs will be recorded. The investigational team will promptly report any AE/SAE as required per federal guidelines.

8.3 UNANTICIPATED PROBLEMS

8.3.1 DEFINITION OF UNANTICIPATED PROBLEMS

This protocol uses the definition of Unanticipated Problems as defined by the Office for Human Research Protections (OHRP). OHRP considers unanticipated problems involving risks to participants or others to include, in general, any incident, experience, or outcome that meets all of the following criteria:

1. Unexpected in terms of nature, severity, or frequency given (a) the research procedures that are described in the protocol-related documents, such as the IRB-approved research protocol and informed consent document; and (b) the characteristics of the participant population being studied;
2. Related or possibly related to participation in the research (“possibly related” means there is a reasonable possibility that the incident, experience, or outcome may have been caused by the procedures involved in the research); and
3. Suggests that the research places participants or others at a greater risk of harm (including physical, psychological, economic, or social harm) than was previously known or recognized.

8.3.2 UNANTICIPATED PROBLEMS REPORTING

The PI will report unanticipated problems (UPs) to the reviewing IRB. The UP report will include the following information:

- Protocol identifying information: protocol title and number, PI’s name, and the IRB project number
- A detailed description of the event, incident, experience, or outcome
- An explanation of the basis for determining that the event, incident, experience, or outcome represents an UP
- A description of any changes to the protocol or other corrective actions that have been taken or are proposed in response to the UP

To satisfy the requirement for prompt reporting, UPs will be reported using the following timeline:

- UPs will be reported to the IRB as soon as possible, but no later than 10 working days after the investigator first learns of the event

8.3.3 REPORTING UNANTICIPATED PROBLEMS TO PARTICIPANTS

Following IRB review of any unanticipated problems, the PI will follow the IRB’s recommended actions. This may include, but is not limited to, modifying the informed consent document or process, re-consenting current participants, providing information to past or current participants (e.g. whenever the information may relate to the participant’s willingness to continue participants), and modifications to the protocol/research plan.

9 STATISTICAL CONSIDERATIONS

9.1 STATISTICAL ANALYSIS PLAN

Aim 1: To assess the feasibility, acceptability, and fidelity of implementation of the Outreach-ER program we will begin by measuring the absolute number of potential care dyads of care partners (CP) and PLWD contacted for recruitment and the number of those who consent and enroll. These will be used to calculate the overall rate of program registration. The feasibility of collecting CP provided data will be evaluated by quantifying the missingness in the registration materials as well the response rate to the two questionnaires. Fidelity of the intervention will be assessed by describing CP attendance rates, length of intervention, and number of sessions as recorded by Outreach-ER staff. Completion patterns will be summarized overall and stratified by patient demographics. Any differences in intervention fidelity associated with CP and PLWD demographics will be described and discussed. Acceptability of the intervention will be assessed using data gathered through the post-intervention interview. The interviews will be transcribed, and recurring themes will be identified by the study team. If a participant withdraws before completion of the intervention this data will be solicited via telephone contact. Table 1 gives an example of how counts will be utilized throughout Aim 1 to describe the recruitment, enrollment, and adherence.

Table 2.

	Counts for feasibility	Use in analysis
Participants contacted	N	Total number of attempted recruits
Participants who enroll and consent	a	Recruitment rate: a/N
Participants who start Outreach-ER programming	b	Participation rate: b/N, compare to a/N
Participants who complete intervention (7+ visits)	c	Completion rate: c/b, used as main progression criteria Overall successful enrollment rate: c/N
Number who complete each intervention visit – k = 1, ..., 7	dk	Session specific completion rate: dk/b
Number who complete each questionnaire – m = 1,2	em	Questionnaire specific response rate: em/a and/or em/b if a ≠ b

Aim 2: The completeness of the CES-D-10, ZBI-12, and PSS outcomes will be quantified by calculating the rate of CPs that respond to all items on each scale (CES-D-10: 10 items, ZBI: 12 items, PSS: 10 items) at each assessment. The rate of completion for both scales will be presented overall and stratified by questionnaire and by CP demographics. Preliminary efficacy analysis will utilize the total scores for the CES-D-10 (range: 0 to 30), ZBI (range: 0 to 48), and PSS (range: 0 to 40) calculated for all completed questionnaires. All outcomes will be summarized at both questionnaire timepoints using means and/or

medians, as appropriate. Change over the study timeframe (Q2-Q1) will be calculated for each CP and summarized for the sample. To evaluate change in efficacy outcomes, the pre and post scores of each instrument will be compared using paired t-tests. If there is no difference in outcomes, we expect Scorepre = Scorepost.

To determine the feasibility of collecting utilization outcomes, the proportion of enrolled CP/PLWDs who are eligible and consent to research access will be calculated. We will collect utilization data from the EHR including number of inpatient, outpatient, and ER visits for the PLWD in the 6 months before and the 3 months during as well as after participation. These counts will be summarized to describe the patterns in utilization associated with participating in the Outreach-ER programming.

Sensitivity analysis will remove those who do not complete the intervention (early withdrawal or <6 sessions). All analysis will be performed in SAS 9.4 and significance determined using a two-sided alpha of 0.05.

To explore the feasibility of obtaining online consent for research access to CP healthcare utilization records. healthcare utilization as an outcome in a full-scale ePCT. Any differences in CP/PLWD demographics between enrollees who opt-in and those who do not will be assessed.

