9.2 POWER ANALYSIS OR STATEMENT OF PRECISION

Sample size rationale: The sample size is largely determined by the logistics of the pilot award funding and time period. We plan to enroll up to 30 dyads. While this pilot is not formally powered for efficacy, we estimate that our sample size would allow detection of a 2-point change in CES-D-10 scores associated with the intervention and CES-D-10 score standard deviation of 4, with 80% power and a two-sided alpha of 0.05. Table 2 provides estimates of the current study's expected effect size with a range of assumptions for SD value (2 to 6) as well as for a reduced sample size our drop out rate reaches 20%.

Table 3. Effect size estimates for pilot study with a range of variation and enrollment assumptions

Effect Size: Difference in CES-D-10 change		
SD	N = 30	N = 24
2	1.1	1.2
4	2.1	2.4
6	3.2	3.6

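### No step collects the second CES-D-10, ZBI-12 and PSS from care partners who stop before Visit 9, and the only sensitivity analysis cannot show what their absence does to the result

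*Combined protocol and SAP*

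**What the plan says.** - **Withdrawal contact.** Section 9.1 (Aim 1) bases acceptability on the post-intervention interview and its themes, and then adds: "If a participant withdraws before completion of the intervention this data will be solicited via telephone contact". The nearest thing that the sentence can refer to is the interview data.
- **When the scales are collected.** They appear in the schedule twice: at baseline (section 7.2, Visit 2) and at Visit 11 (section 7.4). Visit 11 is dated "15-30 DAYS AFTER FINAL INTERVENTION VISIT 9/10". Visits 4 to 10 are each timed from the visit before (sections 7.3.2 to 7.3.8). Section 7.4 lets staff give the survey by telephone or video to people who cannot use email.
- **Main efficacy analysis.** Section 9.1 (Aim 2) takes total scores from all completed questionnaires and compares pre and post scores by paired t-test. It gives no method for a missing second score.
- **Sensitivity analysis.** "Sensitivity analysis will remove those who do not complete the intervention (early withdrawal or <6 sessions"). No other is planned.
- **Completion and response.** The counts table in 9.1 defines completion as seven or more visits. It reports each questionnaire's response against all enrolled, and/or all who start.
- **Dropout.** Section 9.2 considers 20% dropout only as a smaller sample, N = 24 instead of 30.

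**The concern.** A paired test uses only care partners with both scores. If the second score is tied to reaching Visit 9, those who stop earlier drop out of the efficacy result by design, even when they could be reached by telephone and would be willing to answer. Three things are at stake.

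1. The pre-post change may describe those who stayed rather than those who enrolled. It is plausible that the more burdened stop early, which would favour apparent benefit.
2. Agreement between the main and sensitivity analyses could be read as robustness when both use nearly the same people.
3. Aim 2 asks whether outcomes can be collected at all. A low response at the second questionnaire would partly reflect the absence of a scheduled request, and would mislead the planning of the larger study.

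**Working it through.** **1. The plan's own figures.** Inputs from section 9.2 are a power of 80% at the two-sided 5% level, the sample size ("We plan to enroll up to 30 dyads"), and the target effect, given as "detection of a 2-point change in CES-D-10 scores associated with the intervention and CES-D-10 score standard deviation of 4". Taking the SD as that of the change, and solving the paired t-test (noncentral t) for the difference at 80% power:

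| SD | N = 30, computed | Table 3 | N = 24, computed | Table 3 |
|---|---|---|---|---|
| 2 | 1.06 | 1.1 | 1.19 | 1.2 |
| 4 | 2.12 | 2.1 | 2.39 | 2.4 |
| 6 | 3.18 | 3.2 | 3.58 | 3.6 |

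All six entries reproduce. The N = 24 column is 30 x 0.8, so dropout enters the plan only as lost precision (2.12 to 2.39 points at SD 4).

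**2. Who can have a second score.** The non-optional intervention visits are 3, 4, 5, 6, 7, 8 and 9, which is seven. The counts table indexes visits 1 to 7 and sets completion at seven or more. Visit 9, the earliest anchor for Visit 11, is therefore the seventh visit. A dyad that follows the sequence reaches a dated second questionnaire only by completing. A non-completer enters the paired test only by skipping visits and still reaching Visit 9, or by being given a questionnaire outside the schedule.

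**3. What the sensitivity analysis can show.** Suppose 6 of 30 stop before Visit 9, have no second score, and nobody else skips visits. The main analysis has 24 pairs. Removing the 6 leaves the same 24. The two results are identical whatever happened to the 6, so their agreement carries no information about them.

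**4. Response rate.** In the same example, with all 30 enrolled and started, the second-questionnaire rate cannot exceed 24/30 = 80%, even if no one refuses.

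**5. Size of a possible bias.** Let p be the proportion without a second score, m the mean change in those with one, and D how many points worse the mean change is in those without (higher scores are worse).

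Mean change in all enrolled = (1 - p) x m + p x (m + D) = m + p x D.

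The observed m thus differs from the all-enrolled mean by p x D. With p = 0.2, and m = -2.0 assumed for illustration:

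| D | p x D | All-enrolled change | Meaning |
|---|---|---|---|
| -2 | -0.4 | -2.4 | stoppers improve by 4; benefit understated |
| 0 | 0 | -2.0 | same change in both groups |
| 2 | 0.4 | -1.6 | stoppers do not change |
| 3 | 0.6 | -1.4 | stoppers worsen by 1 |
| 4 | 0.8 | -1.2 | stoppers worsen by 2 |

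**6. Effect on the test.** The plan has "significance determined using a two-sided alpha of 0.05". If the true mean change in all 30 is 0, the 24 with both scores have mean change -0.2 x D, and the SD is 4, the paired t-test rejects 5.6%, 7.6%, 10.9% and 15.6% of the time for D = 1, 2, 3 and 4, against a nominal 5%. D is an assumption throughout; no figure in the documents fixes it.

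**The case against.** The strongest reply is that the plan does not restrict efficacy to completers. The stated set is all completed questionnaires, and a sensitivity analysis that removes non-completers presupposes that some are in the main one. Section 7.5 keeps participants active unless withdrawn, section 5.6.2 has staff reschedule missed visits, and section 8.1.5 makes the number of touch points flexible. A poorly attending dyad might therefore still receive Visit 11. On the scales for withdrawers the text is silent; it does not forbid collecting them, and the interview and scales belong to the same visit. Efficacy is exploratory and not formally powered, the main progression criterion is the completion rate, and response rates are reported, so readers will see how many second scores are missing.

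Most of this stands, and it limits the point. A reader might infer that the plan adopts a completers-only rule. It does not; the restriction follows from the schedule. A reader might also infer that the pre-post change is biased towards benefit by a known amount. The documents do not support that either: nothing says that early stoppers are more burdened, the 20% is a contingency rather than an expected rate, and some withdrawals follow a newly met exclusion criterion (section 5.6.1), such as a move to a nursing home, whose effect on care-partner scores is unknown.

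The reply does not supply a date or a step for the second questionnaire when a dyad stops before Visit 9. Nor does it let an analysis that only removes people reveal anything about those already absent. A reported response rate shows how many are missing, not how they differ.

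**Conclusion.** The point holds as a gap in data collection and in the sensitivity analysis. Followed as written, the plan leaves most early stoppers without a second score, rests the paired t-tests mostly on intervention completers, and checks them with an analysis that nearly repeats the first for the three scales. It also lowers the second-questionnaire response rate for a reason unrelated to willingness.

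The bias may plausibly favour benefit, but neither its size nor its direction can be derived. At 20% missing it is 0.2 x D points. For scale, 0.4 to 0.8 points compares with the 2.4 points that the plan gives as detectable at N = 24 and SD 4. These figures assume that all of the 20% lack a second score and, for the rejection rates, an SD of change of 4. Because efficacy is preliminary, this should be corrected but does not undermine the pilot's main progression criterion.

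**What to change.** 1. **Collection (sections 7.4 and 9.1).** For dyads that stop before Visit 9, date the second questionnaire from the time of stopping. Administer the CES-D-10, ZBI-12 and PSS in the telephone contact already planned, where the care partner agrees and can be reached. Telephone administration is already an accepted mode at Visit 11.
2. **Main analysis.** Keep it as stated, on everyone with both questionnaires. It will then include these scores.
3. **Sensitivity analysis.** Add one that keeps every care partner with a baseline score, under a range of assumed changes where the second is missing: for example the same change as completers, no change, and worsening. A single no-change imputation is not enough, since it never tests worsening and understates variance. A two-timepoint mixed model alone is not enough either, since it assumes data missing at random.
4. **Labelling.** Call the removal of non-completers a per-protocol summary. Its cut at fewer than six sessions and the completion definition of seven or more visits leave a dyad with six unclassified unless it counts as an early withdrawal; the two must be reconciled.

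Cost: wording changes, plus about 15 to 30 minutes per call, going by the time allowed for the baseline survey in section 7.2. The timing of the second questionnaire becomes less uniform for early stoppers, and those lost to follow-up still cannot be reached, so item 3 is needed even if item 1 is adopted. At most, with second scores from all 30 rather than 24, the detectable change at SD 4 returns from 2.39 to 2.12 points.

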7.2 BASELINE (VISIT 2) (WITHIN 10 DAYS OF VISIT 1)

- This is a virtual visit
- A REDcap survey is sent via email including the outcome measures CES-D-10, PSS, ZBI-12
- In the case of participants unable to do via email, research staff will conduct this survey via a telephon/video visit
- This visit is about 15-30 minutes.

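### For the baseline questionnaire, one of the two permitted response rates, e1/b, has the wrong denominator: it exceeds e1/a by the factor a/b and can pass 100%

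*Combined protocol and SAP*

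**What the plan says.** The counts table under Aim 1 in section 9.1 (captioned Table 2) sets up these quantities:

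- a: "Participants who enroll and consent"
- b: "Participants who start Outreach-ER programming"
- em: "Number who complete each questionnaire", for m = 1 and 2, with no restriction to starters

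The rate built from them is "Questionnaire specific response rate: em/a and/or em/b", and the entry ends with the condition that a and b differ. One formula serves both questionnaires.

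The study schedule fixes when each count arises. Section 7.2 places the first survey (CES-D-10, PSS, ZBI-12) at "BASELINE (VISIT 2) (WITHIN 10 DAYS OF VISIT 1"), Visit 1 being the consent visit. Section 7.3.1 then describes Visit 3 as the "Initial visit by Amplio consultants", which is where the program begins. Section 7.4 places the second survey at Visit 11, after the last intervention visit. Section 3 lists the questionnaire response rate among the Aim 1 endpoints.

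**The concern.** A response rate should divide those who responded by those who were asked. Those asked to complete Questionnaire 1 are the enrolled, because at Visit 2 nobody has yet started the program. Dividing by b puts people into the numerator who may never enter the denominator. In the table's other rates (a/N, b/N, c/b, c/N, dk/b and em/a) the numerator is a subset of the denominator; e1/b is the exception.

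The cell brings in em/b when a and b differ, which is also when e1/b goes wrong. The table allows for such a gap, since it asks for b/N to be compared with a/N. A result above 100% would be noticed. A result at or just below 100% would not, and it could make baseline data collection look more complete than it was. The pilot is meant to inform a larger study, so the feasibility of collecting these data is one of the things it should report correctly.

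**Working it through.** **Inputs.** The plan states no response rate and no expected b or e1, so there is no printed figure to reproduce. Section 9.2 gives the planned enrollment: "We plan to enroll up to 30 dyads". I take a = 30, with one care partner per dyad answering the questionnaires. The values of b and e1 are assumptions, varied to show the range. The N = 24 in section 9.2 is a 20% dropout scenario for the pre-post comparison, not an estimate of losses between consent and Visit 3; b = 24 below is only an illustration.

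**Formulas.** Let s be the number of starters who completed Questionnaire 1, and treat starters as a subset of the enrolled.

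1. Rate among the enrolled: e1/a. It cannot exceed 100%, because e1 ≤ a.
2. Rate as permitted by the cell: e1/b = (e1/a) × (a/b). When b < a, this exceeds e1/a by the factor a/b, and it passes 100% whenever e1 > b.
3. Rate among starters: s/b. At most a − b responders can be non-starters, so s lies between max(0, e1 − (a − b)) and min(e1, b). Since s ≤ e1, e1/b is never below s/b, and it is too high by (e1 − s)/b.

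**Results, a = 30.**

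| b (assumed) | e1 (assumed) | e1/a | e1/b | possible range of s/b |
|---|---|---|---|---|
| 30 | 27 | 90% | 90% | 90% |
| 29 | 30 | 100% | 30/29 = 103% | 100% |
| 27 | 30 | 100% | 30/27 = 111% | 100% |
| 27 | 27 | 90% | 27/27 = 100% | 24/27 to 27/27, 89% to 100% |
| 24 | 30 | 100% | 30/24 = 125% | 100% |
| 24 | 24 | 80% | 24/24 = 100% | 18/24 to 24/24, 75% to 100% |
| 24 | 20 | 66.7% | 20/24 = 83.3% | 14/24 to 20/24, 58% to 83% |

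The first row shows that the two rates agree when a = b. The row with b = 24 and e1 = 24 shows the less visible failure: e1/b is 100% although six of the 30 enrolled did not respond. If five of the six non-starters were among the responders, only 24 − 5 = 19 of the 24 starters responded, which is 79%.

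**Questionnaire 2.** Visit 11 follows the intervention, so those who reach it are ordinarily starters. Then e2 is contained in b, and e2/b is a sensible rate. The defect is specific to m = 1.

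**The case against.** The strongest reply is that a valid rate is already in the cell. It lists em/a first, and the condition can be read as attaching only to em/b: report em/a and, if a and b differ, consider em/b as well. On that reading an analyst could use a for Questionnaire 1 and b for Questionnaire 2 without departing from the table. The text also introduces the table as an example. The counts a, b and em are all in it, so if they are reported any reader can form e1/a. Aim 2 separately examines item completeness of each scale at each assessment, although it names no denominator.

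Most of this stands. A reader might infer that the plan has no valid baseline response rate once a and b differ, or that it requires e1/b. The documents support neither: em/a remains available, and e1/b is permitted, not mandated. The 79% case is also somewhat contrived, because it needs five starters without a baseline survey alongside five non-starters who completed one.

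What remains is that the wording lets e1/b be reported alone, with the choice left open until the data are known. Even reported beside e1/a, e1/b is neither the rate among the enrolled nor the rate among starters. Example or not, this table is the only place where the endpoint's denominator is given. Counting only starters in the numerator would cure the problem, but the table does not say to do so.

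**Conclusion.** The point holds as a defect in one permitted option for Questionnaire 1. When b < a, e1/b overstates the response among the enrolled by the factor a/b: 30/27 = 1.11 in the example with b = 27, and 30/24 = 1.25 with b = 24. It exceeds 100% whenever e1 > b.

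This rests on three readings: starters are a subset of the enrolled; the baseline survey is offered to all who enroll; and Visit 2 precedes Visit 3, which follows from the visit numbering and the baseline label, not from an explicit rule that the survey must be finished first. The size depends entirely on a gap between a and b that the documents do not predict, and it is zero if everyone enrolled starts.

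A reader might also infer that the decision to proceed to a larger study is at risk. It is not: the table names c/b as its main criterion for progression, and no threshold or test uses em/b. This is a minor correction to a descriptive endpoint.

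**What to change.** Replace the content of that cell with fixed definitions and delete the and/or:

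- Questionnaire 1: e1/a.
- Questionnaire 2: e2/a for all enrolled and, among starters only, e2/b.
- Wherever b is the denominator, count only starters in the numerator. If a baseline rate among starters is also wanted, it is s/b as defined above, not e1/b.

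Every rate is then bounded by 100%, and the useful starters-only rate for Questionnaire 2 is kept. The cost is an edit to one table cell. No new data are needed, because enrollment, program start and questionnaire completion are already to be counted.
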